Using a Stage Model approach (20), the primary aim of this study is to examine the feasibility and acceptability of a resilience intervention for chronic pain among older adults. Intervention modules will specifically engage hope, self-efficacy, positive affect, and pain acceptance as these factors demonstrated the strongest relationships with clinical pain, disability, and psychological functioning from the PI's previous work (NIH K99 Award). Chronic low back pain (cLBP) will be the targeted population given that it represents the most debilitating and therapeutically-challenging pain condition among geriatric populations. We will conduct a pilot study to test the feasibility and acceptability of the intervention in this patient population (primary aim), explore whether the intervention engages the proposed resilience targets (i.e., hope, self-efficacy, positive affect, pain acceptance), and assess whether changes in these factors result in improvements in pain outcomes (i.e., NIH Science of Behavior Change approach (21)). Achievement of these aims will provide a strong framework for future intervention research examining mechanisms that promote adaptive health and pain-related functioning in aging populations.

Specific Aim 1: *Conduct a pilot test to examine feasibility, acceptability, and tolerability of a resilience intervention for older adults with cLBP.* We will assess adherence and retention rates, and evaluate ratings of acceptability through brief assessments and eliciting qualitative feedback from participants at post-intervention. **Hypothesis 1.** Individuals in the resilience intervention will report high adherence to and satisfaction with the intervention.

Specific Aim 2: *Assess whether a resilience intervention facilitates improvements in hope, self-efficacy, positive affect, and pain acceptance and whether changes in these processes result in improved pain-related outcomes.* Intervention modules will be adapted from the existing positive psychology literature and validated self-report measures will be used to verify engagement in the specific resilience targets. **Hypothesis 2.** We hypothesize that a resilience intervention will improve pain severity, pain interference, negative affect, and quality of life by increasing hope, self-efficacy, positive affect, and pain acceptance.

7. Research Plan:

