
Participant payments will be made according to the following schedule: Baseline Assessment (\$60), Intervention Sessions 1-6 (\$20), Intervention Session 7 (\$60), and an additional \$15 for completion of the 3-month follow-up assessment (total max payment=\$255). This is comparable to subject remuneration for studies of similar time commitment and invasiveness at our institution. Participants will receive partial payment if they do not complete the entire study. In addition, for participants traveling more than 25 miles
IRB Project #: 201901927
IRB Version: 12/16/2021

each way to complete study visits, we will reimburse some travel expenses at up to the federal mileage rate (total max travel reimbursement=\$300). Payments for participation will occur after completion of each study session and will be handled through the University of Florida's Human Subject Payment Program.

Session 1 (Baseline):

Demographic and Medical History Questionnaire. All participants will complete a through demographic and medical history form. We will assess self-reported duration of back pain, comorbid conditions, and current medication use. This medical history information will be reviewed with the participant by the study PI or other training study staff to ensure eligibility and that items are completed accurately. Health status will also be reviewed with each participant during subsequent study sessions to ensure eligibility.

Vitals/Physical Measurements. Height will be assessed to the nearest cm using a wall stadiometer and body weight to the nearest 0.1 kg using a digital scale. Calculation of BMI will be determined by weight in kilograms divided by height in meters squared. Blood pressure will also be recorded for all participants.

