Statistical Methods. The goal of the study will be to target 50 participants for the pilot intervention. Accounting for a conservative 20% attrition rate, we will recruit an additional 10 participants (Total $N=60$). This sample size is feasible and will provide stable estimates of dropout rates, feasibility, and acceptability of the intervention protocol. We anticipate screening an additional 70 participants who may not meet eligibility criteria (i.e., screen failures). **Data Analysis: Specific Aim 1.** The analysis of feasibility, tolerability, and acceptability outcomes will be predominantly conducted with descriptive statistics, with means and standard deviations reported. To assess feasibility, we will calculate a ratio between participants enrolled versus the number of participants commencing treatment. Tolerability will be examined by measuring completion rates (i.e., participants completing all seven sessions of the intervention). Participant acceptability of the intervention will be assessed through treatment credibility ratings and satisfaction with the program (59). Chi-square tests and between-group t -tests will be used to compare group differences in baseline characteristics between completers and participant dropouts. **Specific Aim 2.** To assess change in primary study outcomes (i.e., pain severity, pain interference, negative affect, quality of life), mean differences from pre- to post-intervention will be calculated using paired samples t -tests. Clinical significance of treatment changes will be determined by identifying participants whose raw change score for each outcome variable is greater than one-half of a standard deviation from their baseline score (60, 61). Using residualized change scores (i.e., difference between the post-intervention value with the pre-intervention score covaried out), Pearson correlations will be computed to examine associations between outcome and treatment target change scores.

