Data and Safety Monitoring. Because this is not a formal clinical trial, a data and safety monitoring board (DSMB) will not be required. In order to ensure data integrity and safety of human subjects, adverse events reported by participants to staff members or the PI will be recorded on the "Adverse Event and Unanticipated Problems form" developed by the University of Florida's Institutional Review Board. This form requires a description of the event, the course of action taken, and specification regarding whether or not the event was: 1) serious (e.g., life threatening, requiring or prolonging hospitalization, resulting in significant disability/incapacity or death); 2) unexpected (e.g., consistent with anticipated potential risks outlined in the study protocol/informed consent); or 3) causally related to the study interventions/procedures. All serious and unexpected adverse events are to be reported to the University of Florida IRB (within 5 working days) and the study's sponsor. Other types of adverse events will be monitored and reported to the University of Florida IRB in the study's annual progress review.

The investigators will review the reported adverse events on a weekly basis to minimize the risk to the study subjects.

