Questionnaires. Participants will fill out several questionnaires about themselves. While these generally carry no associated risks, it is possible that participants might experience some feelings of discomfort or unease when reading or responding to survey questions that are personal. Throughout each questionnaire, participants will be reminded that participation is completely voluntary, and they can refuse to answer any question or can stop at any time. The PI, Co-I, and study interventionists are psychologists and are trained to deal with depression. Any participants whose responses during the group sessions or on the PROMIS Depression Short Form (raw score ≥ 33) indicate severe psychological distress (such as severe depression) will be interviewed by the site PI, Co-I, or other appropriately trained professionals for suicide risk and risk of harm to self and others. Participants will be assisted to the emergency room if danger is imminent or referred to either their physician or a mental health professional if necessary.

Intervention Integrity. To protect participants and maintain treatment integrity, the PI will thoroughly train research assistants/interventionists on the intervention protocol. The intervention will be manualized to augment treatment fidelity and the study PI will be available for consultation/supervision during intervention sessions and will hold weekly supervision meetings with interventionists to review the protocol and ensure treatment compliance. In addition, the Co-I ([name]) is a licensed clinical psychologist who will be available for consultation/supervision during the intervention sessions.

9. Possible Benefits: While persistent pain is common in older adults, chronic low back pain is the leading cause of disability in this population and results in significant impairments in psychosocial and physical functioning. Participation in this research will provide the participant with a first-hand look at pain research and provide them with the opportunity to participate in a new self-management treatment

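### Tolerability, a named part of Specific Aim 1, is measured only by completing all seven sessions, an adherence measure that can miss harm in people who keep attending and counts unrelated dropout as intolerance

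*Combined protocol and SAP*

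**What the plan says.** Section 6 makes tolerability part of Specific Aim 1: "Conduct a pilot test to examine feasibility, acceptability, and tolerability of a resilience intervention for older adults with cLBP". The assessments listed under that aim are these: "We will assess adherence and retention rates, and evaluate ratings of acceptability through brief assessments and eliciting qualitative feedback". Neither adverse events nor distress is mentioned there.

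The only working definition is in section 7, Statistical Methods, under Specific Aim 1: "Tolerability will be examined by measuring completion rates", where completion means "participants completing all seven sessions of the intervention". The analysis is descriptive and sets no threshold. Completers and dropouts are compared on baseline characteristics, but no analysis of reasons for stopping is described.

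Four other places bear on the point:

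- **Payments (section 7, after Participants).** The schedule includes "Intervention Sessions 1-6 (\$20), Intervention Session 7 (\$60" dollars, and "Payments for participation will occur after completion of each study session".
- **Baseline session (section 7).** Health status is reviewed with each participant at later sessions, for the purpose of confirming eligibility.
- **Data and Safety Monitoring (section 7).** Here "adverse events reported by participants to staff members or the PI will be recorded" on an IRB form that captures seriousness, expectedness and causal relation. Serious and unexpected events go to the IRB and the sponsor; the rest go into the annual IRB review.
- **Questionnaires (section 8).** Participants whose responses in group sessions or "on the PROMIS Depression Short Form (raw score ≥ 33) indicate severe psychological distress" are interviewed about risk.

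The Aim 1 analysis draws on none of the safety information in the last three.

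**The concern.** Completing every session describes what a participant did. Tolerability asks what the treatment did to the participant. The two overlap when harm makes someone leave, and they separate in two situations:

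- A participant attends all seven sessions but has a related adverse event, or newly crosses the distress threshold. This person counts as tolerating the treatment.
- A participant stops because of a job change or a house move. This person counts as not tolerating it.

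The result can therefore err in either direction. Since Aim 1 already promises adherence and retention rates, using completion for tolerability as well leaves tolerability without a measure of its own.

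The study is meant to prepare for later intervention research. As written, it plans a completion rate for the next trial but no estimate of how often participants were harmed or distressed. Distress is also foreseeable: participants discuss their personal experience of pain and record negative events at home, and section 8 provides for severe distress arising in group sessions.

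**Working it through.** **1. Payment schedule.** Inputs are from the payments paragraph, reading 20 dollars as the amount per session. The total is 60 + 6 × 20 + 60 + 15 = 255 dollars, which reproduces the stated maximum. The part tied to the seven intervention sessions is 6 × 20 + 60 = 180 dollars, and 180/255 = 71%. Sessions 1 to 6 alone are 120/255 = 47%. Session 7 also collects the post-treatment questionnaires, so its 60 dollars is not purely for attendance. This shows that attendance is paid. It does not show how far payment raises it.

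**2. Sensitivity of the tolerability figure to harm among completers.** The protocol gives no event rate, so this is an illustration. Assume all 60 recruited participants start and 80% complete (the protocol allows for 20% attrition), giving 48 completers. Let k completers have a related adverse event or marked distress.

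- Tolerability as planned = 48/60
- Completion without such an event = (48 − k)/60

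| Assumed share of completers affected | k | Tolerability as planned | Event-free completion |
|---|---|---|---|
| 0% | 0 | 80% | 48/60 = 80% |
| 10% | 5 | 80% | 43/60 = 72% |
| 20% | 10 | 80% | 38/60 = 63% |
| 30% | 14 | 80% | 34/60 = 57% |
| 50% | 24 | 80% | 24/60 = 40% |

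The planned figure does not move because k does not appear in its formula.

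**3. The opposite error.** Under General Overview of Procedures, a participant may miss one session without making it up. That participant follows the attendance rule, yet does not meet a definition that requires all seven sessions. The two sections need to be reconciled. Together with dropout for unrelated reasons, this lowers the tolerability figure without anyone having tolerated the treatment badly.

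**4. What the pilot could say about harm.** With zero related events among n starters, the exact one-sided 95% upper bound is 1 − 0.05^(1/n).

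- n = 60: 1 − 0.05^(1/60) = 4.9%
- n = 48: 1 − 0.05^(1/48) = 6.1%

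The upper limit of a two-sided 95% exact interval, 1 − 0.025^(1/n), is 6.0% and 7.4% respectively. The value 48 stands for a case where only 80% of the 60 start; the protocol does not state how many will. These bounds have their usual meaning only if participants are actively asked about adverse events. A zero from unprompted reporting bounds the reported rate, not the true one.

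**The case against.** A reader might infer that an intervention that upset or harmed its attendees would be reported as well tolerated. The protocol does not support that. It sets no threshold and plans no verdict, so a conclusion of good tolerability would be the reader's own. Harm that makes people leave does lower completion.

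Harm to those who stay also has other routes to view:

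- adverse events are reviewed weekly;
- Aim 2 tests pre-post change in pain, interference, negative affect and quality of life, and its half-standard-deviation rule for individuals is not worded to cover improvement only;
- satisfaction, usefulness and engagement are rated, and qualitative feedback is collected.

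Three further inferences also go beyond the text:

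- **Attendance is driven by payment.** Nothing shows this; the effect of payment is unknown.
- **Adverse events are captured only if volunteered.** The protocol says that participants report them, not that nobody asks, and the per-session health review is a natural prompt.
- **The study will yield no harm rate.** The forms supply a numerator and the starters a denominator. The gap is that no such summary is planned.

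It can also be said that section 8 describes the risks as minimal and that completion is a common proxy in a behavioural pilot. That keeps the point moderate, but low expected risk does not make attendance a measure of harm.

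What stands is narrower. None of these other sources enters the tolerability result, and mean changes in Aim 2 can hide individuals who worsen.

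**Conclusion.** The point holds in limited form. Tolerability is part of Aim 1, and its only measure is adherence or retention under another name. That measure **can** miss related adverse events or new severe distress in people who keep attending, and it counts unrelated dropout as intolerance.

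The size is unknown, because the protocol gives no event rate and no reasons for dropout. The 80% against 40% contrast is the far end of an assumed range with 60 starters and 48 completers. The 4.9% and 6.1% bounds assume zero related events and active questioning. Payment is a secondary remark with no measurable effect from the protocol alone.

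This should be changed, since the information is largely already collected. It does not undermine the feasibility or acceptability results.

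**What to change.** Report completion of the seven sessions as adherence or retention. Report tolerability among all who start treatment as:

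- (a) the number and percentage with any adverse event, and with any related adverse event, each with an exact confidence interval;
- (b) the number newly at or above the existing PROMIS Depression threshold at the planned post-baseline assessments, among those below it at baseline, stating how many were not assessed;
- (c) the number discontinuing, by reason: adverse event, distress or burden, as against unrelated reasons.

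Ask one standard adverse-event question at the existing per-session health review, and record the reason when someone stops.

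**Cost.** Analysis wording, one question and one recorded reason; the adverse-event form, the threshold and the health review already exist. Prompted questioning will bring in more minor events and make the tolerability figure look less favourable.

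**Limits.** The questionnaires are tied to Visits 1 and 8, with mood again at three months, so people who drop out may have no post-baseline score for (b); this is why the unassessed count is needed. With a single arm, new threshold crossings are descriptive and cannot be attributed to the intervention.

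### Chi-square and t-tests of completers against about 12 dropouts say little about selective dropout, whichever way the p-values fall; report standardized differences with intervals and add one Aim 2 sensitivity analysis

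*Combined protocol and SAP*

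**What the plan says.** All of the relevant text is in section 7, Statistical Methods.

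- Sample size: "The goal of the study will be to target 50 participants for the pilot intervention", and then "Accounting for a conservative 20% attrition rate, we will recruit an additional 10 participants", for a total of 60. The reason given for this size is that it "will provide stable estimates of dropout rates, feasibility, and acceptability of the intervention protocol".
- Comparison of leavers and stayers (Specific Aim 1): chi-square tests and between-group t-tests "will be used to compare group differences in baseline characteristics between completers and participant dropouts". No significance level, size of difference that would matter, interval estimate or consequence of the result is stated.
- Completion is described as "participants completing all seven sessions of the intervention". Dropout is not defined. The General Overview of Procedures lets a participant miss one session without making it up, so someone can stay in the study and still not be a completer.
- Specific Aim 2: change from before to after the intervention is tested by paired t-tests. The post-treatment questionnaires are completed in Week 7 (Intervention Content). No method for missing post-treatment scores is given.

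**The concern.** A completer-dropout comparison is useful if it shows how far the two groups could differ. A p-value from 48 against 12 does not show that. A difference of half a standard deviation, the size that the plan itself uses to mark clinically significant change, would more often than not be non-significant on any one characteristic. In the other direction, the plan lists more than ten scales and does not say which enter the comparison, so a stray significant result is also likely.

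Two things are at stake. First, dropout is one of the things that this pilot sets out to estimate, and who drops out is part of what the next trial needs to know. Second, the Aim 2 mean change comes from participants with both scores, and the plan offers no other look at whether their result carries over to everyone enrolled.

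**Working it through.** **Inputs.** From Statistical Methods: target 50, attrition 20%, total 60. Assumed, because the plan does not state them: two-sided level 0.05, no multiplicity adjustment, equal SDs, and 80% power as the meaning of detectable.

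**The plan's own figure.** 50 × 1.20 = 60, as stated. At 20% attrition, 60 × 0.20 = 12 leave and 48 remain. If exactly 50 remain, 10 leave. Both splits are carried below.

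**Power of one t-test, 48 v 12.** The standard error of the difference in SD units is √(1/12 + 1/48) = 0.323. With 58 degrees of freedom the critical value is 2.002, so an observed difference must reach 2.002 × 0.323 = 0.65 SD to be significant. This is also the half-width of the 95% interval. Power comes from the noncentral t distribution with noncentrality d/0.323:

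| True difference | Noncentrality | Power |
|---|---|---|
| 0.5 SD | 1.55 | 33% |
| 0.64 SD | 1.99 | 50% |
| 0.8 SD | 2.48 | 68% |
| 0.92 SD | 2.85 | 80% |

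The normal approximation to the last row, (1.96 + 0.84) × 0.323, gives 0.90 SD.

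**Other splits** (difference with 80% power):

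| Dropouts / completers | Difference |
|---|---|
| 6 / 54 | 1.23 SD |
| 10 / 50 | 0.99 SD |
| 12 / 48 | 0.92 SD |
| 20 / 40 | 0.78 SD |
| 30 / 30 | 0.74 SD |

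The last two rows cover the case where missing a single session makes someone a non-completer. The test stays weak under every reading of dropout, and it weakens further as retention improves.

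**Chi-square, 48 v 12** (uncorrected Pearson test, exact enumeration). A characteristic present in 50% of completers and 70% of dropouts is detected with 24% power. For 50% v 80% the power is 49%, and for 50% v 90% it is 81%.

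**Many scales at once.** With no true difference and ten independent scales, the chance of at least one significant result is 1 − 0.95^10 = 40%. By simulation, with all ten scales intercorrelated at an assumed 0.5, it is about 29%. If dropouts are truly 0.5 SD worse on all ten, at least one test is significant in about 80% of studies at correlation 0.5, and about 88% at 0.3.

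**Size of the effect on Aim 2.** With 12 of 60 lost, the completers' baseline mean differs from the full-sample mean by (12/60) × d: 0.10 SD for d = 0.5, and 0.18 SD for d = 0.92. That is a shift in a baseline mean. If dropout depends only on that characteristic and the relation is linear, the shift in mean change is the correlation of the characteristic with change times this figure. The documents give no such correlation. At an assumed 0.3 the shifts are 0.03 and 0.06 SD of change; at 0.5 they are 0.05 and 0.09. For scale, the standard error of a mean change from 48 pairs is 1/√48 = 0.14 SD of change.

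**The case against.** The strongest case against the point has four parts.

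- **Large imbalance is not usually missed.** At 0.8 SD a single test has 68% power, and non-significance is the likelier result only below about 0.64 SD. This stands.
- **The check is not one test.** Broadly worse dropouts would produce at least one significant result most of the time. A reader might infer that selective dropout would usually be reported as no difference, but the plan's own list of measures does not support that. The reply is that a study with no selection also produces a significant result in 29% to 40% of cases, so one significant p-value does not separate the two situations well.
- **The purpose is not stated.** The comparison sits under Aim 1, where it may only describe who leaves. The plan never says that non-significance will be taken as reassurance for Aim 2, and that reading should not be attributed to it. This also stands. Even as description, though, estimates with intervals serve better than p-values.
- **The harm is small and the design is a pilot.** The 0.10 to 0.18 SD figures are not biases in a planned estimate, and the step to mean change shrinks them. This stands and sets the severity.

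**Conclusion.** The point holds for each test taken singly, and for what a set of such tests can show. With about 12 dropouts, one baseline comparison reaches 80% power only at 0.92 SD (1.23 SD with 6 dropouts), and chance findings across ten scales are common. P-values alone are therefore a poor account of selective dropout, and the plan adds nothing else alongside the paired analysis.

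The documents do not support the stronger claims that selective dropout would mostly go unseen, that the investigators will treat non-significance as proof of balance, or that Aim 2 is materially biased. The effect on mean change is unknown and probably modest.

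The figures rest on the assumed two-sided 0.05 level, the 20% attrition rate, and dropouts being the 12 who leave; a range of splits leads to the same conclusion. Minor severity: a cheap improvement for a single-arm pilot.

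**What to change.** 1. Define completer and dropout, so that the compared groups are clear and can be set against those with and without a Week 7 score.
2. In place of the tests, or beside them, report each baseline characteristic as a standardized difference (a difference in proportions for categorical items) with a 95% confidence interval. State that non-significance will not be interpreted as absence of selection.
3. Pre-specify one sensitivity analysis of the Aim 2 mean change that uses the baseline data of all enrolled participants and adjusts for a small set named in advance, for example baseline outcome score, age and sex. A likelihood-based repeated-measures model would do this. It assumes that, given those variables, missing scores do not depend on their unseen values.

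Two additions are tempting and should be left out. One is a fixed imbalance flag such as 0.25 SD: with 48 v 12 and no true difference, an observed difference exceeds it about 44% of the time for each variable. The other is adjusting for, or weighting by, whatever the data flag; with 12 dropouts this would follow chance.

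The cost is a few sentences, one table and one extra analysis, with no new data. The intervals will be wide, about ±0.65 SD with 12 dropouts, and showing that plainly is part of the benefit.
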